10.3.7.1. Lactate

Lactate levels will be measured during the controlled fasting challenge (Section [10.4.1](#)) at the time points specified in the Schedule of Events ([Table 1](#)). A blood sample for venous lactate will be collected through an indwelling catheter (central or peripheral) at the beginning of the controlled fasting challenge and approximately every 60 minutes (± 5 minutes) until glucose

levels are at or below 70 mg/dL (≤ 3.9 mmol/L). Once glucose levels are at or below 70 mg/dL (≤ 3.9 mmol/L), a blood sample for lactate will be collected approximately every 30 minutes (± 5 minutes) until the subject's glucose level drops below 54 mg/dL (< 3.0 mmol/L), the subject experiences symptoms of hypoglycemia per the Investigator's discretion, or the fast reaches 15 hours without hypoglycemia, whichever occurs first.

Lactate samples should be sent to the local laboratory (STAT sample) and results should be available within 30 minutes or less of the blood collection. Samples should be prepared and transported to the local laboratory in accordance with the site's standard procedures.

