During the fast, subjects may not ingest any food or drink other than water. The controlled fasting challenge will end when the subject's glucose level decreases to < 54 mg/dL

(< 3.0 mmol/L) or when the subjects experience signs and symptoms of hypoglycemia, or when the fast reaches 15 hours without hypoglycemia, whichever occurs first. The stop time of the controlled fasting challenge will be recorded. At the end of the controlled fasting challenge, the subject's hypoglycemia should be treated per the institution's standard procedure, which may include providing the subject with a meal, cornstarch, or IV glucose, if medically indicated.

In cases where the controlled fasting challenge is terminated prematurely before the subject reaches a glucose level of < 54mg/dL or without the subject experiencing signs and symptoms of hypoglycemia, or due to any deviation in the fasting challenge protocol, an ad hoc fasting challenge may be scheduled within 6 weeks from the scheduled fasting challenge.

Laboratory sample collection before and during the controlled fasting challenge

On the morning of inpatient visit for the controlled fasting challenge, after vital signs and other non-interventional assessments have been performed, samples will be collected for standard clinical chemistry (including lipid levels), hematology, coagulation panel, and urinalysis. These samples should be collected at least 2 to 4 hours after the subject's last meal and sent to the central lab. A sample for STAT AST and ALT level analysis will also be collected at this time and sent to the local laboratory; the Investigator or delegated subinvestigator should review the results before starting the controlled fasting challenge.

Total urine voided over the 24-hour period starting at the time of inpatient admission will be collected during the controlled fasting challenge.

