Blood samples for measurement of cortisol, ACTH, free fatty acids, glucagon, insulin, C-peptide, growth hormone, IGFBP1, alanine and ketone levels (3-hydroxy butyrate) will be collected at the beginning (ie, immediately after the post-dinner dose of cornstarch, or immediately after dinner for subjects who do not take a post-dinner dose of cornstarch) and end of the controlled fasting challenge, or more frequently at the Investigator's discretion. A final sample for glucose, lactate, growth hormone, IGFBP1, ACTH and cortisol measurement will be collected 30 minutes after the end of the controlled fasting challenge. Samples should be prepared and transported to the local laboratory in accordance with the site's standard procedures.

Blood samples for STAT analysis of glucose and lactate will be collected through an indwelling catheter (central or peripheral) at the following time points:

- At the beginning of the fast (ie, immediately after the post-dinner dose of cornstarch, or immediately after dinner for subjects who do not take a post-dinner dose of cornstarch)
- Approximately every 60 minutes (\pm 5 minutes) until the glucose level decreases to \leq 70 mg/dL (\leq 3.9 mmol/L)
- Approximately every 30 minutes (\pm 5 minutes) until the glucose level decreases to < 54 mg/dL (< 3.0 mmol/L) or when the subjects experience signs and symptoms of hypoglycemia, or when the fast reaches 15 hours without hypoglycemia, whichever occurs first

Samples should be prepared and transported to the local laboratory in accordance with the site's standard procedures. To ensure the safety of the study subjects, results from these tests should be available within 30 minutes after the blood sample collection. Capillary glucose will be performed at the same time points as blood samples for STAT analysis of glucose and lactate.

Results of the capillary glucose and readings from CGM at corresponding time points will be noted on a controlled fasting challenge results sheet.

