Plots for individual patient profile of CFC duration and change from baseline in CFC duration by visit will be provided. Additional plots will include CFC duration (and change from baseline) and indicators for inappropriately high insulin level or inappropriately low cortisol levels during the CFC if that data is collected during the CFC. Insulin response is deemed inappropriate if ≥ 25 $\mu\text{IU/mL}$ at the start of the challenge or $> 2\mu\text{IU/L}$ at the end of the challenge. Cortisol response is deemed inappropriate if < 10 $\mu\text{g/dL}$ at the end of the challenge. Plots will also be provided for normalized CFC duration (by the amount of pre-CFC cornstarch).

Pre-CFC whole blood lactate and rate of rise of lactate during the CFC (calculated as the slope between the lactate value at the start of CFC and peak lactate value during the CFC, expressed as mmol/L/h) and change from baseline will be summarized by visit. Pre-CFC analyte value is the value collected nearest to the start time of the CFC and within ± 30 minutes of start time of CFC. End-CFC analyte value is the value collected nearest to the end time of the CFC and within ± 30 minutes of end time of CFC. Peak analyte value during the CFC is the maximum analyte value observed any time from the start time of CFC to the end time of the CFC and including pre-CFC and end-CFC analyte values.

Similarly, pre-CFC plasma glucose and rate of decline of glucose during the CFC and change from baseline will be summarized by visit. Trough analyte value during the CFC is the minimum analyte value observed any time from the start time of CFC to the end time of the CFC, including pre-CFC and end-CFC values (defined above). Rate of decline of glucose will be calculated as the slope between the pre-CFC glucose value and trough glucose value during the CFC, expressed as mg/dL/h .

In addition, plots for individual patient profile of glucose and lactate levels during CFC will be presented by study visits. Plot for individual patient profile of glucose and ketones levels during CFC will be presented by study visit where that data was collected.

A listing of metabolic lab parameters (glucose, lactate, ketones, free fatty acids, alanine), and hormonal lab parameters (cortisol, ACTH, glucagon, insulin, C-peptide, growth hormone, IGFBP1) collected before and during the controlled fasting challenges will be provided.

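### The SAP's end-of-fast window admits the sample scheduled 30 minutes after the fast, which can enter the lactate peak and rate of rise when no in-fast draw is closer to the stop

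*SAP*

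**What the plan says.** SAP 6.8.1 sets the rule: "End-CFC analyte value is the value collected nearest to the end time of the CFC". The draw must lie no more than 30 minutes before or after that time. The SAP does not restrict candidates to draws made before the stop or before treatment, and it gives no tie-break. The peak and trough are taken over the interval from start to end of the CFC, with the End-CFC value added to the set. The lactate rate of rise is the slope from the start value to the peak; the glucose rate of decline is the slope from the pre-CFC value to the trough. Both rates, and their changes from baseline, are summarized by visit.

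Protocol 10.4.1 adds one more draw to the in-fast schedule, for six analytes (cortisol, ACTH, IGFBP1, growth hormone, lactate and glucose). This draw "will be collected 30 minutes after the end of the controlled fasting challenge", and no tolerance on that time is stated. The same section says that hypoglycemia at the end of the challenge is treated by local procedure, "which may include providing the subject with a meal, cornstarch, or IV glucose, if medically indicated".

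In-fast glucose and lactate are drawn every 60 ± 5 minutes until glucose is at or below 70 mg/dL, then every 30 ± 5 minutes (Protocol 10.3.7.1 and 10.4.1). A fast can also stop on symptoms, at the Investigator's discretion; the schedule lists no extra glucose and lactate draw at such a stop. Hormones have a planned end-of-fast draw, qualified by the words if possible in Table 1 footnote 9 and in Protocol 10.3.7.2.

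**The concern.** Peak and trough are meant to describe the fast. Because the window extends 30 minutes past the stop, a value obtained after the fast, and perhaps after a meal or glucose, can enter them by being labelled End-CFC. Choosing the nearest value prevents this only when an in-fast draw lies closer to the stop than the post-end draw.

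What is at stake is a descriptive metabolic readout: chiefly the lactate peak and the rate of rise built on it. Lactate is a tertiary endpoint, and the endocrine and metabolic response to fasting is a tertiary objective. Cohorts were enrolled with 3 subjects each, so one misassigned value carries a third of the weight in a full cohort's mean.

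**Working it through.** The documents give no figure to reproduce. The check applies the SAP rule to the protocol's draw times.

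**Definitions.** Let d be the minutes from the last in-fast draw to the recorded stop, and p the minutes from the stop to the post-end draw. The post-end sample is selected if p ≤ 30 and d > p.

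**Inputs from the documents.** Window ±30 minutes, read as including its limits; p nominally 30; draw interval L of 60-65 minutes in the first phase and 30-35 in the second (the interval and its upper tolerance); local laboratory result within 30 minutes of the draw.

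**Assumptions, because the documents give no distributions.** The stop falls uniformly within the draw interval, so d is uniform on 0 to L; no draw is taken at the stop; p is either exactly 30 or uniform on 25-35.

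**With p = 30.** A last draw 0-29 minutes before the stop wins; at exactly 30 there is an unresolved tie; beyond 30 the post-end sample is the only candidate.

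**Formulas.**
- p = 30: probability = (L − 30)/L when L > 30, otherwise 0.
- p uniform on 25-35: probability = (1/10) × ∫ from 25 to 30 of (L − p)/L dp = 0.5 − 13.75/L.

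| Symptom stop, no draw at the stop | p = 30 | p uniform 25-35 |
|---|---|---|
| Hourly phase, L = 60 | 30/60 = 50% | 0.5 − 0.229 = 27% |
| Hourly phase, L = 65 | 35/65 = 54% | 0.5 − 0.212 = 29% |
| 30-minute phase, L = 30 | 0% | 0.5 − 0.458 = 4% |
| 30-minute phase, L = 35 | 5/35 = 14% | 0.5 − 0.393 = 11% |

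**Other situations.**
- Draw taken at the stop: d = 0, so 0%.
- Post-end draw always later than +30: outside the window, so 0%.
- Glucose-triggered stop, recorded when the result arrives, lag assumed uniform on 0-30 minutes: 0% with p = 30; 0.5 − 13.75/30 = 4% with p uniform on 25-35.
- End-of-fast hormone draw missed and no other hormone draw in the window: 100% with p = 30; 50% with p uniform on 25-35.

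**Effect on each output once the sample is selected.**
- *Lactate rate of rise.* The peak is a maximum, so it changes only if the post-end value exceeds every in-fast value. Illustration with assumed values: start 2.0 and in-fast peak 3.0 mmol/L at an 8-hour stop give (3.0 − 2.0)/8 = 0.125 mmol/L/h. A post-end value of 3.5 at 8.5 hours gives 1.5/8.5 = 0.18; a value of 5.0 gives 3.0/8.5 = 0.35; a value below 3.0 leaves 0.125.
- *Glucose rate of decline.* The trough is a minimum, so a glucose raised by treatment will rarely displace it.
- *Cortisol flag.* It uses cortisol at the end of the challenge, and cortisol is in the post-end sample. It is exposed only if the planned end draw is missing and the flag is programmed from the End-CFC value, which the SAP does not state.
- *Insulin flag.* Insulin is not in the post-end sample.
- *ACTH, growth hormone, IGFBP1.* SAP 6.8.1 plans only a listing.
- *CFC duration.* It comes from the recorded start and end times, so the analyte rule does not touch it.

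**The case against.** The strongest reply is that the nearest-value rule works in ordinary conduct. A fast ended by low glucose has a triggering draw, a 15-hour stop falls on the nominal sampling grid, and hormones have their own end draw. In those cases an in-fast value is normally chosen. A fast that reaches 15 hours without hypoglycemia may also involve no treatment before the post-end sample. This stands, and makes the defect conditional.

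A reader might go further than the documents allow in four ways.
- *That post-meal values will be reported as the end-of-fast response.* No by-visit summary of the End-CFC value is planned; it acts as a candidate for peak or trough.
- *That the cortisol flag is generally compromised.* SAP 6.8.1 ties the indicator to data collected during the CFC, and the glucose and lactate draw intervals do not govern cortisol.
- *That the secondary endpoint is contaminated.* It is not.
- *That about half of symptom-ended fasts are misclassified.* Half is the chance that no in-fast draw lies in the window, for hourly sampling with L = 60. It equals the chance of selecting the post-end sample only if that sample is drawn at exactly +30 and the limit is inclusive. It also applies only to symptom stops during hourly sampling, whose share of challenges the documents do not give.

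The gap in the rule remains: no sentence in the SAP keeps the post-end sample out.

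**Conclusion.** The point holds in limited form. As written, the End-CFC rule can select the post-end sample when no in-fast draw is closer to the stop, chiefly at a symptom stop during hourly sampling or, for hormones, when the end draw is missed. The material consequence is a possibly inflated lactate peak and altered rate of rise in the affected challenges.

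Its frequency cannot be derived from the documents. The 27-54% range is conditional on a symptom stop in the hourly phase, no draw at the stop, a uniformly distributed stop time and the two assumed timings of the post-end draw. If the window excludes its limit, a draw at exactly +30 is not admitted, and only early draws matter. The slopes of 0.18-0.35 against 0.125 mmol/L/h are illustrations, not estimates. All analyses are descriptive, so no error rate or power is involved. This is a minor clarification worth making before the outputs are programmed.

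**What to change.** Amend the definitions in SAP 6.8.1 as follows: exclude the scheduled 30-minute post-end sample, and any sample drawn after treatment or feeding, from the End-CFC, peak and trough values; take as End-CFC the nearest remaining sample within 30 minutes of the end; present the post-end sample under its own time-point label. State that the cortisol flag uses this End-CFC value, if that is the intent, and add a tie-break.

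A simpler rule that accepts only draws at or before the recorded stop would also remove the problem, but it could discard a genuine end-of-fast draw taken a few minutes after the recorded stop and before treatment.

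The text change is small. The cost is missing End-CFC values, mainly in symptom-ended fasts on hourly sampling. Under the assumptions above, with no draw between the stop and treatment, the value would be absent in 50-54% of such stops in the hourly phase and 0-14% in the 30-minute phase. The lactate and glucose slopes can still be computed from the in-fast draws. Protocol 10.4.1 does not say that the time of treatment is recorded, so where it is not, the exclusion will rest on the scheduled time-point label.

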6.8.2. Use of Cornstarch (or Glycosade)

Data from both studies 401GSDIA01 and 401GSDIA02 will be included in this analysis. The prescribed and actual daily amount (g) and frequency of cornstarch over time, change from baseline and percent change from baseline will be summarized by study visit and provided in the listings. Summary will also be provided for daily cornstarch intake (g) per kg of body weight

over time. Summary may be provided at last available study visit for a subject if deemed appropriate. In addition, the percent change from baseline in prescribed and actual daily cornstarch amount by study visit will be plotted for each subject. Further, daytime cornstarch intake and nighttime cornstarch intake will be summarized. Daytime cornstarch frequency and nighttime cornstarch frequency will be summarized.

Prescribed and actual daily frequency of cornstarch by study visit will be plotted for each subject along with information on daily amount of cornstarch. Daily daytime and nighttime frequency of cornstarch (prescribed and actual) will be plotted by visit for each subject.

Further, average duration of dosing interval and change from baseline will be analyzed separately for daytime and nighttime doses. For each dose, duration of dosing interval is calculated as the time (in hours) from current dose to the next dose.

Data collected at a scheduled visit within an analysis window of +/- 14 days of the target day for a visit up to Week 52, within an analysis window of +/- 21 days of the target day for visits post Week 52 and up to Week 104 and within an analysis window of +/- 42 days of the target day for visits post Week 104 will be included in the analysis. If such a scheduled visit is not performed, data collected at the nearest unscheduled visit (if any) completed within that analysis window will be included.

6.8.3. GSDIa Diet (Non-Cornstarch)

Data from both studies 401GSDIA01 and 401GSDIA02 will be included in this analysis. The prescribed and actual daily GSDIa non-cornstarch diet parameters and change from baseline values will be summarized by study visit. Diet parameters will include total calories, amounts of individual macronutrients (carbohydrates, non-utilizable sugars, protein, and fat), % of total calories from individual macronutrients, and non-utilizable sugars as % of total carbohydrates. Total calories in diet will be derived from individual macronutrients as follows:

Total calories (Kcal)= 4 x amount of carbohydrates (g)+ 9 x amount of fat(g) + 4 x amount of protein (g).

Summary may be provided at last study visit if deemed appropriate. Individual subject listing of GSDIa diet data will be provided.

Data collected at a scheduled visit within an analysis window of +/- 14 days of the target day for a visit up to Week 52 and within an analysis window of +/- 21 days of the target day for visits post Week 52 and up to Week 104 and within an analysis window of +/- 42 days of the target day for visits post Week 104 will be included in the analysis. If such a scheduled visit is not performed, data collected at the nearest unscheduled visit (if any) completed within that analysis window will be included.

Further, total calories from diet and cornstarch and % of total calories (cornstarch and diet combined) from individual macronutrients will be summarized by study visit. Total calories (Kcal) from cornstarch will be derived as 3.75 x amount of cornstarch (g).

Plot of mean % of total calories from individual macronutrients by study visit will be provided.

6.8.4. Continuous Glucose Monitoring

Continuous glucose monitoring (CGM) device data was collected for only cohort 3 and 4 in Study 401GSDIA01. It will be collected for all subjects in Study 401GSDIA02. Available data from both studies 401GSDIA01 and 401GSDIA02 will be included in this analysis. CGM values less than 40 mg/dL or greater than 400 mg/dL will not be included in the analysis because they are not considered as reliable values being outside the Dexcom G6 reportable range of 40-400 mg/dL.

Percentage of glucose values in different glucose ranges (<54, <60, <70, 60-120, 70-120, >120 mg/dL) together with cornstarch intake (in grams) will be plotted by visit for each subject along with the actual cornstarch use at the visit. CGM data in 4 weeks prior to the visit will be used to calculate the percentage of glucose values in any range. Percentage of glucose values in any glucose range for a visit is calculated as number of glucose values in that range in a 4-week period prior to the visit, divided by total number of glucose values in that 4-week period and multiplied by 100. Further, mean percentage of glucose values in different glucose ranges (<54, <60, <70, 60-120, 70-120, >120 mg/dL) together with mean actual cornstarch intake (in grams) will be plotted by visit for each cohort.

Time spent below 70 mg/dL in 4 weeks prior to the visit will be plotted by visit for each subject. Time duration (in minutes) of glucose values spent in a range is calculated as sum of all the time intervals where glucose value is in that range. Time interval for any glucose value is calculated as the difference between collection time of that glucose value and the next collection time. Glucose values are usually collected approximately every 5 minutes, however if the glucose value is missing at any collection time the last available glucose value prior to the collection time will be carried forward if that value is collected within 15 minutes.

Number and total duration of hypoglycemic events in 4 weeks prior to the visit will be plotted by visit for each subject together with actual cornstarch use at a visit. A hypoglycemic event is defined as a series of at least two sensor glucose values less than 54 mg/dL that are at least 15 minutes apart with no intervening values of 54 mg/dL or more. The end of a hypoglycemic event is defined as at least two sensor glucose values > 70 mg/dL that are at least 15 minutes apart with no intervening values <70 mg/dL. Similar plots will be provided for nocturnal hypoglycemic events. Summary of number and duration of hypoglycemic events in 4 weeks prior to the visit will be provided.

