6.9.6. Symptomatic Hypoglycemic Events

The number of subjects reporting symptomatic hypoglycemic events as captured in eCRF and number of events will be summarized by visit. Data from both studies 401GSDIA01 and 401GSDIA02 will be included in this analysis.

Details of the symptomatic hypoglycemic events will be provided in a listing.

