8. LIST OF PLANNED TABLES AND FIGURES

List of planned tables, figures, and listings will be included in the shell document which will be maintained separately.

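### Dropping CGM readings below 40 mg/dL turns the planned <54, <60 and <70 percentages into 40-53, 40-59 and 40-69, and understates low glucose if the dropped readings are true lows

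*SAP*

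**What the plan says.** SAP section 6.8.4 (Continuous Glucose Monitoring) sets the exclusion before any summary is defined: "CGM values less than 40 mg/dL or greater than 400 mg/dL will not be included in the analysis". The reason it gives is that such readings lie beyond what the sensor can report, 40 to 400 mg/dL, and so are treated as unreliable.

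It then lists the ranges to be plotted: <54, <60, <70, 60-120, 70-120 and >120 mg/dL. The three low ranges have no lower bound. For each visit the percentage is the count of readings in the range over the preceding four weeks, "divided by total number of glucose values in that 4-week period and multiplied by 100". The percentages are plotted by visit for each subject, and as means for each cohort, beside cornstarch intake.

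The same section also plans time below 70 mg/dL and CGM hypoglycemic events: "Number and total duration of hypoglycemic events in 4 weeks prior to the visit will be plotted by visit for each subject". An event starts with "at least two sensor glucose values less than 54 mg/dL that are at least 15 minutes apart" and no value of 54 or more in between.

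Section 6.8.4 describes no below-range category, no count of removed readings and no sensitivity display. Under SAP section 8, the list of planned tables, figures and listings "will be included in the shell document which will be maintained separately"; the shells were not available to me, so a footnote there cannot be ruled out.

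**The concern.** The label and the content do not match. A plot headed <54 would cover 40-53 only, and the readings left out are the lowest ones recorded.

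The stated reason supports not using the numeric value of an out-of-range reading. It does not by itself support removing the reading from a display that needs only its category. If the sensor is right that glucose is below its floor, the reading belongs in <54, <60 and <70. The documents do not say whether such readings are true lows or artefact, or how the device stores them.

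At stake is how glucose control reads over follow-up. Glucose homeostasis is a tertiary objective, and these plots set time at low glucose against cornstarch intake. If deep lows became more frequent, the plotted percentage could show only part of the rise.

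**Working it through.** The documents give no CGM percentage to reproduce, so the check is algebra on the SAP's own formula, followed by worked figures. **All glucose frequencies below are assumed.**

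**Inputs from SAP 6.8.4:** the 40 and 400 mg/dL limits, the range cut-offs, the percentage formula, readings about every 5 minutes, and the event rule.

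**Direction.** Let N be all readings in the four weeks, L those below the cut-off, and d those below 40 (all of which belong to L). Keeping everything gives L/N. The SAP rule gives (L - d)/(N - d). The difference is

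L/N - (L - d)/(N - d) = d(N - L) / [N(N - d)],

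which is positive whenever d > 0 and L < N. If the denominator were taken before the exclusion, the result would be (L - d)/N, lower still.

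**Could dropped readings above 400 reverse this?** With h dropped high readings and a true percentage p below the cut-off, the SAP figure exceeds the true one only if h/d > (100 - p)/p. That is 32.3 at p = 3, 19 at p = 5 and 9 at p = 10.

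**Level.** Take a true percentage below 54 of p = 3, with a share q of those readings below 40. The SAP figure is 100 × (p - pq)/(100 - pq).

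| q | SAP figure (true 3.00) |
|---|---|
| 5% | 2.85 |
| 10% | 2.71 |
| 25% | 2.27 |
| 50% | 1.52 |

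**Artefact.** In the 25% case, pq = 0.75. If a share a of the sub-40 readings is artefact, the correct figure is 100 × (3 - 0.75a)/(100 - 0.75a): 3.00 at a = 0, 2.63 at a = 0.5 and 2.27 at a = 1. The SAP figure of 2.27 is right only when all are artefact. Keeping every reading (3.00) is right only when none is.

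**Change over time.** Per day, true % = 100 × (time <40 + time 40-53)/1440, and SAP % = 100 × (time 40-53)/(1440 - time <40). Start with 5 min below 40 and 15 min at 40-53: true 1.39, SAP 1.05. Let time below 40 rise to 30 min.

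| Time at 40-53 at the end | True % | SAP % | Share of true change shown |
|---|---|---|---|
| 15 min (unchanged) | 3.13 | 1.06 | 1% |
| 45 min | 5.21 | 3.19 | 56% |
| 90 min | 8.33 | 6.38 | 77% |

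**In range.** With 900 min/day at 70-120 and 30 min/day below 40, the true value is 900/1440 = 62.50%. The SAP shows 900/1410 = 63.83%.

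**Events.** I applied the start and end rules with and without the sub-40 readings to 240 assumed profiles per floor. These used 5-minute sampling; a start at 100 mg/dL; falls of 1, 1.5, 2 or 3 and recoveries of 1, 2, 3 or 4 mg/dL/min; 15, 30 or 60 min at the floor; and five sampling phases. At floors of 38, 36, 30 and 20 mg/dL, 216, 219, 213 and 222 profiles kept the same event start and end. The other 24, 21, 27 and 18 lost the event. Every loss had a recovery of at least 3 mg/dL/min, where the 14 mg/dL between 40 and 54 is crossed in 14/3 = 4.7 min or less, so a 5-minute reading can miss it. These are shares of an assumed grid, not expected rates.

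**Time below 70.** The effect here is unclear. The SAP carries a value forward for up to 15 minutes when a reading is missing, but does not say whether a removed reading counts as missing. If it does, three constructed traces kept 45 of 45, 35 of 50 and 25 of 45 minutes.

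**The case against.** The exclusion is stated openly, with a reason, directly before the ranges, so it can be read as limiting every range to the device's reportable span. On that reading the gap is a label, and a footnote in the shells may already close it. The harm depends on facts the documents do not give. The 1% scenario is a limiting case, because a fall below 40 and the recovery from it normally pass through 40-53.

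Other displays also limit the damage. In the grid, 89% to 93% of profiles keep their event unchanged. For symptomatic events, SAP section 6.9.6 says: "The number of subjects reporting symptomatic hypoglycemic events as captured in eCRF and number of events will be summarized by visit". Fasting-challenge duration comes from the eCRF, with venous glucose or symptoms as the end criteria. Section 6.8.4 plans no CGM change from baseline, and Cohorts 1 and 2 have no CGM data from Study 401GSDIA01. Finally, counting readings that the SAP calls unreliable could overstate low glucose.

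Most of this stands as a limit on size, and the 1% figure should not be read as typical. It does not remove the point. Disclosing the rule does not make a range of 40-53 into <54, and nothing else in the SAP corrects the percentages. The risk of overstating is real, which is why both displays are needed.

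**Conclusion.** The concern holds. By the SAP's own rule and formula, the three low ranges are truncated at 40. For any number of dropped true lows the percentages fall, unless dropped readings above 400 greatly outnumber them. The relative loss is close to the share of lows that lie below 40.

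The actual size cannot be found from the documents and may be nil. It depends on how often readings fall below 40 and how many of those are artefact. The consequence is confined to supplemental, descriptive displays: nothing is tested, and the primary and secondary endpoints are unaffected. It should be fixed because a plot headed <54 would mislead its reader and the correction is cheap. Confidence is medium, because the frequency and nature of the readings, and the shells, are unknown.

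**What to change.** In SAP section 6.8.4:

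- Keep out-of-range readings as categories, without using their numeric value. A reading below 40 counts in <54, <60, <70, time below 70 and the event rule; a reading above 400 counts in >120.
- Keep both kinds in the denominator, and do not replace them by carry-forward.
- Report the percentage of readings below 40 and above 400 by subject and visit.
- Show the planned exclusion as a sensitivity display, in case some readings are artefact.
- If the exclusion stays as the main analysis, label the ranges 40-53, 40-59 and 40-69.

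The cost is SAP wording and small programming changes, with no new data. The downside is that low-glucose figures may look less favourable. If many sub-40 readings are artefact, the main figure would be too high, and the sensitivity display and the counts would let a reader judge that.
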